6.12. Rescue Therapy

A rescue algorithm is provided to minimize subjects having an inadequate response to the treatment for their anemia for an extended period of time and to enable consistency in the application of rescue therapy across the study. Details are provided in [Table 6](#).

This rescue algorithm **does not** apply to subjects with a low Hgb as a result of an acute or subacute event with an identifiable cause (e.g., GI bleed, blood loss due to surgery or vascular access). In these cases, treatment should be directed to the specific cause and randomized treatment will be continued. If a subject is transfused as part of the treatment, then the randomized treatment will be maintained at the current dose (unless Hgb is ≥ 12 g/dL which requires a dose hold).

Table 6 Rescue Algorithm for Anemia Management

Evaluate Subject for Rescue if: HemoCue Hgb remains <9 g/dL (at a scheduled study visit, Week 4 onwards) despite three ¹ consecutive dose increases above the starting ² or post-rescue ³ dose (where HemoCue Hgb is <9 g/dL prior to each dose increase) OR HemoCue Hgb is <7.5 g/dL despite a dose increase at the prior study visit.	
Step 1: Initial Intervention	While continuing randomized treatment (increase dose if HemoCue Hgb <7.5 g/dL; otherwise maintain current dose), intervene with one or more of the following as dictated by clinical comorbidities 
 - Single course of IV iron up to 1000 mg (in addition to the iron management criteria) - Transfusion of up to two units of packed red blood cells (PRBC) if clinically indicated - Allow additional 4 weeks on randomized treatment (NOTE: this is a required choice; can be combined with either or both of the above).
Step 2: Rescue	Check HemoCue Hgb 4 weeks ±1 week from last study visit; earlier checks of Hgb may be obtained to advise further intervention as clinically indicated. Randomized treatment should be permanently discontinued and the subject should be rescued according to local clinical practice if either, 
 - If HemoCue Hgb remains <9 g/dL despite initial intervention based on the average of two HemoCue Hgb values⁴ 
OR
 
 - More than two units of PRBC were needed for transfusion (and was not related to acute bleeding).

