1. Two consecutive dose increases if starting/post-rescue dose is daprodustat 12 mg, epoetin alfa 42000 U per week, or darbepoetin alfa 200 µg over 4 weeks; one dose increase if starting/post-rescue dose is daprodustat 16 mg, epoetin alfa 48000 U per week, or darbepoetin alfa 300 µg over 4 weeks; and no prior dose increase if starting/post-rescue dose is daprodustat 24 mg, epoetin alfa 60000 U per week, or darbepoetin alfa 400 µg over 4 weeks (top dose).
2. For subjects who have switched from HD to PD who are randomized to rhEPO, the baseline dose for the purposes of the rescue algorithm is the new darbepoetin alfa dose.
3. For subjects who previously were evaluated for rescue and who are able to continue in the trial, "post-rescue" dose is the dose of randomized treatment that a subject is receiving at the study visit after initial intervention.
4. Repeat HemoCue Hgb at the same study visit to confirm Hgb (using the same sample); take average of 2 values.

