12.2. Appendix 2: Secondary and Exploratory Objectives/ Endpoints

Objectives	Endpoints
Secondary Objectives	Secondary Endpoints (tested for superiority¹, no multiplicity adjustment)

 To compare daprodustat to rhEPO on additional CV safety endpoints 	
 All-cause mortality, CV mortality, fatal or non-fatal MI, fatal or non-fatal stroke² MACE or hospitalization for HF² (recurrent events analysis) CV mortality or non-fatal MI² All-cause hospitalization All cause hospital re-admission within 30 days MACE or hospitalization for HF or thromboembolic events² Hospitalization for HF² Thromboembolic events²

 To compare daprodustat to rhEPO on Hgb variability 	
 Hgb change from baseline to Week 52¹ N (%) responders, defined as mean Hgb within the Hgb analysis range 10-11.5 g/dL during EP % time Hgb in analysis range (10-11.5 g/dL) during the evaluation period (EP, Week 28 to 52) and during the maintenance period (MP; Week 28 to end of trial) (non-inferiority analysis that will use a margin of 15% less time in range)¹

 To compare daprodustat to rhEPO on BP 	
 Change from baseline in SBP, DBP and MAP at Week 52 and at end of treatment Number of BP exacerbation events per 100 patient years N (%) with at least one BP exacerbation event during study

 To compare daprodustat to rhEPO on the time to rescue (defined as permanently stopping randomized treatment due to meeting rescue criteria). 	
 Time to stopping randomized treatment due to meeting rescue criteria

 To compare daprodustat to rhEPO on HRQoL and Utility score 	
 Mean change in SF-36 HRQOL scores (Physical Component Score (PCS), Mental Component Score (MCS) and 8 health domains) between baseline and Weeks 8, 12, 28, 52, of particular interest are the changes from baseline in the vitality and physical functioning domains at Wk 28 and 52 Change from baseline in Health Utility (EQ-5D-5L) score at Week 52 Change from baseline in EQ VAS at Week 52

 To compare daprodustat to rhEPO on the symptom severity and change 	
 Change from Baseline at Wk 8, 12, 28, 52 in PGI-S

Objectives	Endpoints

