12.6. Appendix 6: Randomized Treatment Dose Adjustment Schemes

HemoCue Hgb (g/dL) at current study visit ¹	HemoCue Hgb change since last study visit ¹	Randomized Treatment Dose Adjustment ⁵
<7.5 ²	Any change	Repeat Hgb and average values ⁶ ; if confirmed, increase to the next higher dose step
7.5 to <9.5	Decreasing or No change ⁷	Increase to the next higher dose step
7.5 to <9.5	Increasing ⁸	Maintain dose
≥9.5 to <10 at two consecutive visits	Decreasing or No change	Increase to the next higher dose step
≥9.5 to ≤11.5	Any change	Maintain dose
>11 to ≤11.5 at two consecutive visits	Increasing or No change	Decrease to the next lower dose step
>11.5 to <12	Decreasing	Maintain dose
>11.5 to <12	Increasing or No change	Decrease to the next lower dose step
≥12 ³	Any change	Repeat Hgb and average values ⁶ ; if confirmed, temporary hold the dose and re-check Hgb at next study visit ¹ ; restart at one dose step lower when Hgb <11.5 g/dL and provided it has been at least 2 weeks from the prior study visit.
Any	>2 g/dL increase over 4 weeks (>1 g/dL increase over 2 weeks ⁴)	Repeat Hgb and average values ⁶ ; if confirmed, decrease to the next lower dose step
Any	>2 g/dL decrease over 4 weeks (>1 g/dL decrease over 2 weeks ⁴)	Repeat Hgb and average values ⁶ ; if confirmed, increase to the next higher dose step

1. "Study visit" refers to mandated study visits (every 4 weeks through Week 52; then every 12 weeks). From Week 52 onwards, additional study visits to check Hgb and dispense randomized treatment (where directed by the IRT system) are required under the following circumstances (additional visits have a visit window of ±1 week):

- When Hgb at last study visit is outside of the target range, i.e., <10 or >11 g/dL: Visit 4 weeks later to assess for dose adjustment.
- When the dose of randomized treatment is changed or restarted in the previous 12 weeks ±1 week: Visits every 4 weeks for 12 weeks.
- When a medication that is a moderate CYP2C8 inhibitor (i.e., clopidogrel, teriflunomide, deferasirox) is started, stopped, or the dose is changed: Visits every 4 weeks for 12 weeks.
- When the investigator determines it clinically necessary to evaluate a subject sooner than 12 weeks later: Visit 4 weeks later to assess for dose adjustment.
- For subjects changing dialysis modality from HD to PD: Visits every 4 weeks for 12 weeks.

2. This rule applies to any mandated visit or unscheduled visit, provided it has been at least 2 weeks from the prior study visit.

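### After a Table 6 Step 1 transfusion, the Appendix 6 rate-of-rise row can take a dose step from a subject just evaluated for inadequate response, even if donor cells caused the rise

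*Protocol*

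**What the plan says.** Section 6.12 separates two situations.

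- **Acute or subacute cause (for example a bleed).** The rescue algorithm does not apply. For these cases the section says "If a subject is transfused as part of the treatment, then the randomized treatment will be maintained at the current dose", with a hold at Hgb 12 g/dL or more as the only exception.
- **Inadequate response.** Table 6 applies if Hgb stays under 9 g/dL despite consecutive dose increases, or is under 7.5 g/dL despite an increase at the prior visit. Step 1 permits "Transfusion of up to two units of packed red blood cells (PRBC) if clinically indicated" and a course of IV iron up to 1000 mg. It sets the dose as follows: "increase dose if HemoCue Hgb <7.5 g/dL; otherwise maintain current dose". Step 2, at 4 weeks ±1 week, says only when to discontinue: Hgb still under 9 g/dL, or more than two units needed.

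Appendix 6 governs dosing at study visits, and the IRT applies it programmatically in both arms (Sections 4.1 and 6.3.3). One row, valid at any Hgb, covers a rise of ">2 g/dL increase over 4 weeks" and, once confirmed, lowers the dose one step. Neither that row nor the footnotes to Appendix 6 mention transfusion. After Week 52, footnote 1 requires, when Hgb is outside target, "Visit 4 weeks later to assess for dose adjustment".

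Table 6 footnote 3 defines the post-rescue dose as the "dose of randomized treatment that a subject is receiving at the study visit after initial intervention". Footnote 1 counts the increases needed before the next rescue evaluation from that dose.

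**The concern.** A rate-of-rise rule guards against a drug raising Hgb too fast. Appendix 4 lists dose guidance that includes rate of change among the mitigations for excessive erythropoiesis. Transfused cells raise Hgb without erythropoiesis. In a subject whose Hgb has just been under 9 or 7.5 g/dL despite dose increases, a transfusion-driven rise says nothing about whether the dose is too high. The written rule nevertheless lowers it, or cancels the increase Step 1 has just ordered, and the protocol gives the investigator no override.

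What is at stake is the management of known under-responders. There may also be a small effect on the secondary endpoint "Time to stopping randomized treatment due to meeting rescue criteria" in Appendix 2, because the next rescue evaluation is counted from the post-rescue dose.

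**Working it through.** The protocol gives no figure to reproduce. The check applies the written rules to Hgb at the rescue evaluation (H0) and at the 4-week check (H1), in 0.1 g/dL steps.

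**Inputs.** Stay on treatment if H1 ≥ 9.0 (Table 6 Step 2). Step 1 dose: +1 step if H0 < 7.5 and not at top dose, otherwise 0. Rate row: −1 step if H1 − H0 > 2.0 (Appendix 6). Hold if H1 ≥ 12.

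**Row order.** Appendix 6 states no precedence. A rising Hgb of 7.5 to under 9.5, and any Hgb from 9.5 to 11.5, also meet a maintain-dose row. If those rows won, the rate row would never act on its own: above 11.5 and under 12 a rising Hgb already gives a decrease, at 12 or more there is a hold, and under 7.5 there is an increase. The natural reading is therefore that the rate row overrides.

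**Where it fires.** The smallest H1 that triggers the row is the larger of 9.0 and H0 + 2.1.

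| H0 | Rise needed to reach 9.0 | Row fires from H1 |
|---|---|---|
| 6.5 | 2.5 | 9.0 |
| 6.9 | 2.1 | 9.0 |
| 7.0 | 2.0 | 9.1 |
| 7.4 | 1.6 | 9.5 |
| 8.0 | 1.0 | 10.1 |
| 8.9 | 0.1 | 11.0 |

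From 6.9 or lower, 9.0 − 6.9 = 2.1 > 2.0, so every subject who passes Step 2 meets the row (or the hold).

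**Net change, Step 1 plus rate row,** for rises of 0.1 to 3.0 that reach 9.0 or more:

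- H0 7.5–8.9: rise of 2.0 or less, 0 steps (195 of 195 pairs); rise over 2.0, −1 step (150 of 150). For example, 8.4 to 10.4 gives 0 and 8.4 to 10.5 gives −1.
- H0 6.5–7.4, below top dose: rise of 2.0 or less, +1 (15 of 15, all from 7.0–7.4); rise over 2.0, +1 − 1 = 0 (90 of 90).
- H0 6.5–7.4, at top dose: no increase is possible, so a rise over 2.0 gives −1 (90 of 90).

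These counts confirm the logic of the rule. They are not frequencies.

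**Size of one step from top dose.** Daprodustat 24 to 16 mg: 1 − 16/24 = 33.3%. Epoetin alfa 60000 to 48000 U: 1 − 48000/60000 = 20.0%. Darbepoetin alfa 400 to 300 µg: 1 − 300/400 = 25.0%.

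**Can a transfusion reach the trigger from 7.0 upward?** Assume, since the protocol does not say, that each unit leaves 0.5 to 1.5 g/dL at 4 weeks. Two units then give 1.0 to 3.0 g/dL. If iron and drug add *o* g/dL, the row fires when the rise per unit exceeds (2.0 − *o*)/2: above 1.0 for *o* = 0, above 0.75 for *o* = 0.5, above 0.5 for *o* = 1.0. It is reachable but not certain.

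**Next rescue evaluation at 24 mg, if Hgb is under 9 at each later visit.** Table 6 footnote 1 asks for "no prior dose increase if starting/post-rescue dose is daprodustat 24 mg" and one increase from 16 mg. Without the decrease, evaluation comes at the first later visit. With it, evaluation comes at the second visit (about 4 weeks later) if the post-rescue dose is the lowered 16 mg, or at the first if it is the 24 mg on arrival.

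**The case against.** The strongest defence is that the brake is deliberate. A rescue-evaluated subject has usually had recent dose increases, may get another in Step 1, and may receive up to 1000 mg of IV iron. Section 4.4.1 puts pharmacodynamic steady state at almost 3 months, so earlier increases may still be taking effect. A rise over 2 g/dL could be partly drug. The effect is one step and largely self-correcting: a falling Hgb of 7.5 to under 9.5 triggers an increase at the next visit, and after Week 52 a dose change brings visits every 4 weeks for 12 weeks. This stands as a reason to keep the level-based limits and restore the rate row quickly. It does not justify acting on a rise that may come from donor blood.

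A reader might infer that, with identical Hgb values and transfusion, a bleeding subject keeps the dose while an under-responder always loses a step. The documents do not support that. It needs the acute-cause sentence in 6.12 to suspend the rate row at the next visit, and that sentence names no visit. Below top dose, a low under 7.5 also ends at net 0, the same as a maintained dose.

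The IRT specification and the Study Reference Manual are not shown and could contain an exemption. The protocol text does not.

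**Conclusion.** The gap is real and worth correcting, but small. Under the written rules a Step 1 transfusion can cost an under-responder one dose step, or cancel the step just ordered. This is unavoidable, for those staying on treatment and not put on hold, only from a low under 7.0 g/dL. From 7.0 upward it depends on an assumed rise per unit. The net loss of a step is confined to top dose and to lows of 7.5 to 8.9.

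The conclusion rests on the rate row overriding the maintain-dose rows, on a confirmed rise over the 4-week interval, and on no exemption existing outside the protocol. A delay to the next rescue evaluation, worked out only at top dose and about 4 weeks, depends on how Table 6 footnote 3 is read.

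A reader might also infer a bias between arms or a threat to the Hgb or MACE conclusion. Nothing here supports that: the rule is the same in both arms, the protocol gives no rate of Step 1 transfusions, and the secondary endpoint concerned has no multiplicity-adjusted claim.

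**What to change.** Add a footnote to the Appendix 6 row for a rise of more than 2 g/dL over 4 weeks: the row does not trigger a decrease at the first study visit after a transfusion given under Table 6 Step 1, and the 4-week additional visit after Week 52 counts as that visit. The hold at 12 g/dL or more, the row for above 11.5 to under 12, and the increase under 7.5 g/dL still apply. The rate row applies again at the following visit. Cross-reference the footnote in Table 6 Step 2, and confirm that the IRT receives a transfusion flag.

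The cost is one footnote, one cross-reference and a small IRT change. Transfusions are already recorded in the eCRF (Table 7), but the protocol does not show that the IRT sees them. Section 9.2.3 says the study is fully enrolled, so the change would reach only subjects still on treatment. The clinical downside is that a drug- or iron-driven rise hidden by a transfusion is acted on one visit (4 weeks) later, with the level-based limits still in force.

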6.13. Subjects Changing Dialysis Modality

Subjects changing dialysis modality should not be withdrawn from the study, and will continue in the same randomized treatment arm (daprodustat or rhEPO) they were originally assigned. Those subjects randomized to rhEPO who transition from PD to HD (in-center or home HD) will continue on darbepoetin alfa. However, subjects randomized to rhEPO who transition from HD to PD will switch from epoetin alfa to darbepoetin alfa at their next study visit from Week 4 onwards. If this occurs from Week 52 onward, additional visits are required as outlined in [Appendix 6](#).

7. STUDY ASSESSMENTS AND PROCEDURES

Protocol waivers or exemptions are not allowed with the exception of immediate safety concerns. Adherence to the study design requirements, including those specified in the Time and Events Table, are essential and required for study conduct.

This section lists the procedures and parameters of each planned study assessment. The exact timing of each assessment is listed in the Time and Events Table Section 7.1.

Because Hgb levels become more variable with increased time between dialysis sessions, the designated study visit should occur during the dialysis session with the shortest interval from the previous session. Study visit days should be scheduled as follows:

- For subjects on 3-5x/week HD, the designated study visit must not occur on the first dialysis session of the week, i.e., immediately following the longest interval between HD sessions. For example, if on a Monday-Wednesday-Friday schedule, the study visit should be on Wednesday or Friday.
- For subjects on PD, study visits can occur on any day of the week.
- For subjects on 2x/week HD, the study visit must occur on the day of the dialysis session that is closest to the previous session. For example, if a subject receives dialysis on a Monday and Thursday, the study visit should be on the Thursday (2 days from the previous dialysis session) rather than the Monday (3 days from the previous dialysis session).

The Week -4 and Day 1 visits should be completed 4 weeks \pm 1 week after the last visit; however, the total duration of the Screening and Run-In periods (from Week -8 to Day 1) should be 8 weeks \pm 1 week (i.e., 7-9 weeks).

Post-randomization visits should be referenced back to the Randomization visit (Day 1). The visit window for those on randomized treatment for the Week 2 and Week 4 visits is \pm 3 days. The visit window specified for those on randomized treatment from Week 8 onwards is \pm 1 week. However, during the first 52 weeks, to ensure continuity of randomized treatment, study visits must be no more than 5 weeks apart. In exceptional circumstances, minor changes to visit structure may be permitted after consultation with the PPD Medical Monitor.

Study assessments should preferably be done at dialysis centers; however, in some circumstances (i.e., where the dialysis center and research site are not co-located) assessments can be performed at the research site.

Supplementary study conduct information is provided in the SRM. The SRM provides administrative and detailed technical information that does not impact subject safety.

7.1. Time and Events Table

Table 7 Schedule of Assessments Year 1 to End of Study

Protocol activity (visits ± 1 week, except Weeks 2 and 4 which are ± 3 days) All assessments pre-dialysis unless otherwise specified (Note: All visit timings are relative to Day 1)	Day 1 through Week 52							
	Screen Week -8	Run-in Week -4	Day 1 ¹³	Week 2	Full study visit Week 4, 16, 28, 40	Abbreviated study visit Week 8, 12, 20, 24, 32, 36, 44, 48	Week 52	Unscheduled ¹⁰
Informed consent (main study)	X ²²							
IRT system transaction ¹⁷	X	X	X	X	X	X	X	X
Subject reminder, inform site staff of changes in health ¹			X				X	
Check/confirm entry criteria	X		X					
History: medical, hospitalization, transfusion demography, height	X							
Weight (pre- and post-dialysis for in-center HD subjects; between treatments for HHD; at study visits per standard of care for PD) and EDW	X	X	X	X	X	X	X	X
SBP/DBP, HR (pre- and post-dialysis for in-center HD subjects; between treatments for HHD; at study visits per standard of care for PD) (single readings unless otherwise indicated)	X	X	X (triplicate)	X	X	X	X (triplicate)	X
Kt/V _{urea} ¹⁸			X		X		X	
ECG ²			X ²				X	
Ultrasound of kidneys and adrenal glands		X ¹⁶						
Placebo run-in or randomized treatment dispensing (start administration on date treatment dispensed) ¹⁹		X (placebo)	X	X ⁹	X	X	X	X ⁹
Placebo run-in or randomized treatment compliance ¹⁹			X (placebo)	X ¹¹	X	X	X	X ¹¹
Iron therapy, transfusions ³	X	X	X	X	X	X	X	X
Rescue medication(s) for Initial Intervention ^{3,4}					X	X	X	
Females only: estradiol and FSH (if required)	X							
FRP only: Serum pregnancy test ^{5,20}		X	X		X		X	
HemoCue Hgb	X	X	X	X	X	X	X	X
Hematology ⁶	X	X	X		X	Hgb only	X	X
Clinical chemistry ⁶	X		X		X		X	X

Protocol activity (visits ± 1 week, except Weeks 2 and 4 which are ± 3 days) All assessments pre-dialysis unless otherwise specified (Note: All visit timings are relative to Day 1)			Day 1 through Week 52					
	Screen Week -8	Run-in Week -4	Day 1 ¹³	Week 2	Full study visit Week 4, 16, 28, 40	Abbreviated study visit Week 8, 12, 20, 24, 32, 36, 44, 48	Week 52	Unscheduled ¹⁰
Ferritin, total iron, UIBC ⁶	X		X		X		X	
Hepcidin			X		X		X	
HbA1c ⁷ , lipids (non-fasting)			X				X	
hsCRP, iPTH			X		Wk 28		X	
Storage biomarkers ²¹			X		Wk 28		X	
Hospitalization ³ , kidney transplant ³				X	X	X	X	X
Non-serious AEs, SAEs, AEs of special interest, clinical events	X ⁸	X	X	X	X	X	X	X
Review concomitant medications	X	X	X	X	X	X	X	X

Schedule of Assessments Year 1 to End of Study (Continued)

Protocol activity (visits ±1 week) All assessments pre-dialysis unless otherwise specified (Note: All visit timings are relative to Day 1)	Year 2				Year 3				Year 4					Unscheduled ^{10,12}	End of Study ¹⁵	Follow-up (4-6 weeks after stopping randomized treatment)	
	Week 64	Week 76	Week 88	Week 100	Week 112	Week 124	Week 136	Week 148	Week 160	Week 172	Week 184	Week 196	Week 208 ¹⁴				
IRT system transaction ¹⁷	X	X	X	X	X	X	X	X	X	X	X	X	X	X	X	X	X
Weight (pre- and post-dialysis for in-center HD subjects; between treatments for HDD; at study visits per standard of care for PD) and EDW	X	X	X	X	X	X	X	X	X	X	X	X	X	X	X	X	X
SBP/DBP, HR (pre- and post-dialysis for in-center HD subjects; between treatments for HDD; at study visits per standard of care for PD) (single readings unless otherwise indicated)	X	X	X	X	X	X	X	X	X	X	X	X	X	X	X	X	X (triplicate)
Kt/V _{urea} ¹⁸	X		X		X		X		X		X		X				
ECG ²				X				X					X				
Randomized treatment dispensing (start administration on day of dispensing) ^{17,19}	X	X	X	X	X	X	X	X	X	X	X	X	X	X	X ⁹		
Randomized treatment compliance ^{17,19}	X	X	X	X	X	X	X	X	X	X	X	X	X	X	X ¹¹	X	
Iron therapy, transfusions ³	X	X	X	X	X	X	X	X	X	X	X	X	X	X	X	X	
Rescue medication(s) for Initial Intervention ^{3,4}	X	X	X	X	X	X	X	X	X	X	X	X	X				
FRP only: serum pregnancy test ^{5,20}	X	X	X	X	X	X	X	X	X	X	X	X	X			X	X
HemoCue Hgb	X	X	X	X	X	X	X	X	X	X	X	X	X	X	X		
Hematology ⁶	X	Hgb only	X	Hgb only	X	Hgb only	X	Hgb only	X	Hgb only	X	Hgb only	X	X	X	X	X
Clinical chemistry ⁶	X		X		X		X		X		X		X	X	X	X	X
Ferritin, total iron, UIBC ⁶	X	X	X	X	X	X	X	X	X	X	X	X	X			X	X
Hepcidin, HbA1c ⁷ , lipids (non-fasting), hsCRP				X													

Protocol activity (visits ± 1 week) All assessments pre-dialysis unless otherwise specified (Note: All visit timings are relative to Day 1)	Year 2				Year 3				Year 4					Unscheduled ^{10,12}	End of Study ¹⁵	Follow-up (4-6 weeks after stopping randomized treatment)
	Week 64	Week 76	Week 88	Week 100	Week 112	Week 124	Week 136	Week 148	Week 160	Week 172	Week 184	Week 196	Week 208 ¹⁴			
iPTH		X		X												
Hospitalization ³ , kidney transplant ³	X	X	X	X	X	X	X	X	X	X	X	X	X	X	X	X
Non-serious AEs, SAEs, AEs of special interest, clinical events	X	X	X	X	X	X	X	X	X	X	X	X	X	X	X	X
Review concomitant medications	X	X	X	X	X	X	X	X	X	X	X	X	x	X	X	X

iPTH, intact parathyroid hormone; FSH, follicle stimulating hormone; UIBC, unsaturated iron binding capacity; HbA1c, glycated hemoglobin; hsCRP, high sensitivity C-reactive protein; SBP, systolic blood pressure; DBP, diastolic blood pressure; ECG, electrocardiogram; EDW, estimated dry weight

- Health changes include new symptoms or medical problems (e.g., pregnancy, hospitalizations) and changes in medication.
- Day 1 ECG may be performed as early as the Week -4 visit through the Day 1 visit on a dialysis day (if 3 times/week dialysis, cannot be done on the first dialysis session of the week). If performed on Day 1, it must be pre-dialysis and over-read prior to randomization. All other ECGs assessments may be recorded pre or post dialysis and require over-reading.
- Record in eCRF, if applicable.
- See details on Rescue in Section 6.12.
- Repeat pregnancy test prior to placebo run in or randomized treatment re-administration if it is disrupted for >7 days and there was also a lapse in contraceptive use, regardless of the reason for the disruption. If a subject becomes post menopausal (as defined in Appendix 5) during the study pregnancy tests are no longer required.
- See details on hematology and clinical chemistry in Section 7.4.11.
- HbA1c assessment only in subjects with diabetes on Day 1 or diagnosed during the study.
- Only SAEs assessed as related to study participation or a GSK product are collected at this visit. See Section 7.4.3.1 for additional details.
- If dose does not change, then randomized treatment is returned to subject.
- If a subject lost their placebo run-in or randomized treatment, it is not necessary to perform the unscheduled visit assessments other than dispensing placebo run-in or randomized treatment.
- Required only if dose is changed or randomized treatment is dispensed. Compliance checking will be required when a dose of randomized treatment is changed.
- Additional visits to check Hgb and dispense randomized treatment (where directed by the IRT system) are required under the circumstances described in Appendix 6. Hematology and chemistry samples are not required.
- All assessments pre-dose.
- Further visits every 12 weeks as required.
- Investigator will inform subject when to attend this End of Study visit (Section 6.3.4).
- Ultrasound of the kidneys and adrenal glands will be performed as early as 6 weeks prior to the Day 1 visit. If results of kidney and adrenal ultrasound require follow-up testing, then the run-in period can be extended by 1 additional week. A documented ultrasound of the kidneys within the 6 months prior to screening may be used to assess entry criteria,

provided the size and cyst category has been reported. If a more sensitive imaging study [e.g., magnetic resonance imaging (MRI), computed tomography (CT)] has been performed within this timeframe and a report is available, this may be used in place of the ultrasound. See Section 7.4.10.

17. Treatment will be dispensed every 4 ± 1 weeks; an IRT transaction will be required; perform randomized treatment compliance.
18. A historical Kt/Vurea measurement within the last 12 weeks can be used. If a Kt/Vurea measurement is not available, then a urea reduction ratio (URR) measurement is acceptable. Kt/Vurea and URR measurements are not required for daily HHD.
19. In circumstances where the new dose of randomized treatment cannot be dispensed on the day of the study visit, the new dose of randomized treatment can be dispensed at next HD treatment. For visits after Day 1, prior randomized treatment should be continued unless on dose hold, Hgb ≥ 12 g/dL. Compliance is deferred until randomized treatment is returned.
20. **For Argentina ONLY:** Pregnancy testing will be performed every 4 weeks for FRP as required by local law.
21. Biomarker samples will be stored for future analyses for all subjects, except if not permitted by IRB/EC or refused by subject.
22. Informed consent will be obtained prior to any study procedures.

Table 8 Schedule of Assessments for Patient Reported Outcomes, Genetics and Sub-studies

Protocol Activity (visits ± 1 week) (Note: All visit timings are relative to Day 1)	Screening		Day 1 through Week 208								End of Study
	Week -8	Week -4	Day 1	Week 4	Week 8 & 12	Week 16, 20 & 24	Week 28	Week 32, 36, 40, 44, 48	Week 52	Week 100, 148, 208	
Patient Global Impression of Severity (PGI-S) ¹	X		X		X		X		X		
Patient Global Impression of Change (PGI-C) ¹					X		X		X		
Short Form 36 (SF-36) ¹			X		X		X		X		
EuroQol 5 Dimension 5 Level Health Utility Index (EQ-5D-5L) and EuroQol Visual Analogue Scale (EQ-VAS) ^{1,2}			X		X		X		X	X	X
Healthcare resource utilization (subject reported)				X	X	X	X		X	X	X (& Follow up)
Genetics sample ³			X								
ABPM sub-study (Appendix 12): Informed Consent	X ⁴	X ⁴									
Atrial fibrillation/flutter screening		X ⁵									
24 hour ABPM		X ⁶				X (Week 16)					
Record awake and sleep times		X ⁷				X ⁷ (Week 16)					
PK sub-study (Appendix 13): Informed Consent			X ⁸	X ⁸	X ⁸	X ⁸	X ⁸	X ⁸	X ⁸		
PK assessment				X ⁹	X ⁹	X ⁹	X ⁹	X ⁹	X ⁹		

1. Subjects who are unable to or require assistance to read must not complete the questionnaires.

2. Only in selected countries. See [Appendix 3](#).

3. Informed consent for optional Genetic research should be obtained before collecting a sample. To minimize potential study bias, the genetic sample should be collected on Day 1.

4. Informed consent for ABPM sub-study can be obtained at Week -8 or at the Week -4 visit prior to conducting any ABPM sub-study assessments.

5. Heart rate will be assessed prior to ABPM, subjects with irregular heart beat will undergo an ECG to assess if atrial fibrillation/flutter is present (see Section [12.12.3.3](#).)

6. Baseline ABPM will be performed at any mid-week dialysis visit starting at Week -4 until 1 week prior to randomization (Day 1); the device will be returned at the next visit, which ideally is no later than 1 week prior to randomization to allow for QC of the ABPM.

7. Subject will record sleep and awake times during the ABPM session.

8. Informed consent for PK sub-study can be obtained anytime from Day 1 (once the subjects is confirmed to have been randomized to daprodustat) till Week 52, i.e., last study visit where PK sampling can be obtained.
9. Blood samples will be collected at any single study visit from the Week 4 through Week 52 visit (i.e., PK is collected at one visit only, based on convenience for the subject/site).

Table 9 Schedule of Assessments for Subjects Permanently Discontinuing Randomized Treatment

Protocol Activity All assessments pre-dialysis unless otherwise specified (Note: All visit timings are relative to Day 1)	Early Treatment Discontinuation Visit (within 2 weeks of discontinuing randomized treatment)	Day 1 through Week 52 ⁷	
		Week 4, 16, 28, 40, 52 ± 2 weeks	Unscheduled
IRT system transaction	X		
SBP/DBP, HR (pre- and post-dialysis for in-center HD subjects; between treatments for HDD; at study visits per standard of care for PD) (single readings unless otherwise indicated)	X (triplicate)	X	X
ECG	X		
Iron therapy, transfusions ¹	X	X	X
Serum pregnancy test (FRP only)	X ⁶		
HemoCue Hgb	X	X	X
Hematology ³ ,	X	X	
Clinical chemistry ³	X	X	
Ferritin, total iron, UIBC, hepcidin, lipids, iPTH	X		
Hospitalization ¹ , kidney transplant ¹	X	X	X
Non-serious AEs, AEs of special interest, SAEs, clinical events	X	X	X
Review concomitant medications	X	X	X
Healthcare resource utilization (subject reported)	X		
PGI-S, PGI-C ^{4,9}	X		
SF-36 ^{4,9}	X		
EQ-5D-5L& EQ-VAS ^{4,5,9}	X		
ABPM sub-study (Appendix 12): 24 hour ABPM		X (Week 16)	
Record awake and sleep times		X (Week 16) ²	

Note: see footnotes on next page

Schedule of Assessments for Subjects Permanently Discontinuing Randomized Treatment (Continued)

Protocol activity (visits \pm 2 week) (Note: All visit timings are relative to Day 1)	Year 2 ⁷				Year 3 ⁷				Year 4 ⁷					Unscheduled	End of Study ⁸
	Week 64	Week 76	Week 88	Week 100	Week 112	Week 124	Week 136	Week 148	Week 160	Week 172	Week 184	Week 196	Week 208		
IRT system call															X
SBP/DBP, HR (pre- and post-dialysis for in-center HD subjects, between treatments for HHD and PD subjects) (single readings unless otherwise indicated)	X	X	X	X	X	X	X	X	X	X	X	X	X	X	X
HemoCue Hgb	X	X	X	X	X	X	X	X	X	X	X	X	X	X	X
Hematology ³	X	Hgb only	X	Hgb only	X	Hgb only	X	Hgb only	X	Hgb only	X	Hgb only	X		X
Clinical chemistry ³	X		X		X		X		X		X		X		X
Hospitalization ¹ , kidney transplant ¹	X	X	X	X	X	X	X	X	X	X	X	X	X	X	X
Non-serious AEs, SAEs, AEs of special interest, clinical events	X	X	X	X	X	X	X	X	X	X	X	X	X	X	X
Review concomitant medications	X	X	X	X	X	X	X	X	X	X	X	X	X	X	X

1. Record in eCRF, if applicable.

2. Subject will record sleep and wake time during the ABPM session.

3. See details on hematology and clinical chemistry in Section 7.4.11.

4. Only completed at Early Treatment Discontinuation visit if the randomized treatment discontinuation occurs on or before Week 52

5. Only in selected countries. See Appendix 3.

6. Additional pregnancy test required at subsequent visit. Must be at least 4 weeks after the end of randomized treatment.

7. Phone visits are acceptable in exceptional circumstances.

8. Investigator will inform subject when to attend this End of Study visit.

9. Subjects who are unable to or require assistance to read must not complete the questionnaires.

